7.1 Specification of Safety Parameters

Risks to the individual with AD and caregiver in this study are minimal. There have been no serious adverse events with PA interventions in any of our completed trials, including trials in adults with DS. Increased PA may be associated with minor injuries such as strains and sprains, and the potential for muscle soreness, particularly in the early stages of the PA protocol, may exist.

7.2 Methods and Timing for Assessing, Recording, and Analyzing Safety Parameters

Staff involved in performance of the protocol will continually monitor participants for adverse events throughout all outcome's assessments, exercise sessions, and individual education session. All AEs and SAEs will be recorded in the studies REDCap database.

7.3 Adverse Events and Serious Adverse Events

An adverse event (AE) is as any untoward or unfavorable medical occurrence in a human subject participant, including any abnormal sign, symptom, or disease, temporally associated with the participants' involvement in the research, whether or not considered related to participation in the research. Reported signs and symptoms consistent with normal exercise such as transient work-related dyspnea, flushing, fatigue, sweating, or light soreness of muscles or joints will not be considered AEs.

A serious adverse event (SAE) is defined as any adverse event that results in death, a life-threatening event, inpatient hospitalization, or a permanent disability.

7.4 Reporting Procedures

The MPIs will review and evaluate adverse events within 72 hours. AEs are reported to the DSMB bi-annualy for review, and immediately if unexpected. A summary of these reports is provided to the IRB on an annual basis. Deaths and SAEs are handled in an expedited fashion as follows:

- *Deaths:* All deaths will be reported within 24 hours to the NIA Program Officer, DSMB, and the IRB.

- *Unanticipated SAEs*: When SAEs occur that are unanticipated and related to the intervention, they will be reported to the NIA Program Officer, DSMB, and the IRB within 48 hours of study team's knowledge of the SAE.
- *Other SAEs*: The summary of all other SAEs will be reported to the NIA Program Officer and DSMB semi-annually.

All potential Adverse Events will be collected on an Adverse Event Form. If study staff, tester, participant, or other individual interacting with the participant during the testing visits, group exercise sessions, or individual education sessions reports adverse events or complaints, relevant information will be collected and documented using REDCap.

7.5 Follow-up for Adverse Events

Study team members will follow-up with adverse events at the next exercise session or individual education session until event is resolved.

7.6 Safety Monitoring

This study will use a DSMB. The DSMB consists of three members. Membership consists of individuals who have no financial, scientific, or other conflict of interest with the trial. Written documentation attesting to absence of conflict of interest will not be required as the experimental intervention/manipulation is standard of care. The DSMB includes experts with relevant clinical expertise and understanding of clinical trial methodology, and biostatistics.

8 STATISTICAL CONSIDERATIONS

8.1 Sample Size and Randomization

Eighty participants will be randomized in a 2:2:1 manner to RH (n=32), RL (n=32) and UC (n=16), respectively. We except a standard deviation in daily MVPA of ~ 10 min. for our primary endpoint (12 mos.) based on 12 mo. data from adults with DS who participated in our weight management trial in adults with IDD (DK83538, PI [name]). We will be able to estimate the mean MVPA at each time point (baseline, 3, 6, 9 and 12 mos.) with 99% confidence within ± 5 min. for the RH and RL groups with 32 participants, and with 98% confidence with 24 participants, i.e. allowing for a 25% loss to follow-up. We will be able to estimate the mean MVPA at each time point with 94% confidence within ± 5 min. for the UC group with 16 participants, and with 89% confidence with 12 participants, i.e. allowing for 25% loss to follow-up). Thus, we will have precision to estimate the intervention effects even with a 25% loss to follow-up.

8.1.1 Treatment Assignment Procedures

Cohorts of ~10-20 participants will be recruited and computer randomized. Participants will be stratified by sex and age (18-30 or >30) and then sequentially randomized by the study statistician with 2:2:1 allocation to the RL, RH, and UC arms.

This randomization scheme was selected to include more participants in the group video conferencing arms which, if successful, will be included in a later stage trial examining the effectiveness of increased MVPA using the video conferencing approach on cognitive function and brain health in adults with DS.

Intervention assignments will be concealed in envelopes and delivered to the study coordinator. Participant randomization will be stored on the study Redcap Database.

The study team and the participants will not be blinded to group assignment.

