4.3 Study Enrollment Procedures

Project staff will contact local community agencies serving adults with DS, case managers, and CDDOs by mail/email, provide presentations at CDDO meetings, and text for CDDO newsletters describing the project. Interested parents/guardians, caregivers, or adults with DS will be asked to contact the study coordinator via email, our website (www.ebl.ku.edu), or a dedicated toll-free study phone number that will be included in all recruitment materials. The study coordinator will contact the interested individuals by phone to answer questions and conduct an initial eligibility screen. Zoom calls will be scheduled with those remaining interested, and potentially eligible, to obtain informed consent (participants or guardian and caregivers) and assent (participant) and determine final eligibility based on the DSQIDD scores. Project staff will send a form (fax/email) to the potential participant's PCP which describes the study and requests clearance for participation. Participants found to be ineligible will be provided with written materials describing available resources for increasing physical activity. Project staff will track ineligibility and non-participants of eligible candidates using a REDCAP database. Participants will be stratified by sex and then sequentially randomized by the study statistician with 2:2:1 allocation to the RL, RH, and UC arms.

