5 STUDY INTERVENTIONS

Randomization Cohorts of ~10-20 participants will be recruited and computer randomized. Participants will be stratified by sex and age (18-30 or >30) and then sequentially randomized by the study statistician with 2:2:1 allocation to the RL, RH, and UC arms. This randomization scheme was selected to include more participants in the group video conferencing arms which, if successful, will be included in a later stage trial examining the effectiveness of increased MVPA using the video conferencing approach on cognitive function and brain health in adults with DS. Intervention assignments will be concealed in envelopes and delivered to the study coordinator.

Caregiver role. We will recruit either a parent/guardian or residential support staff, to serve as a study partner for each participant. Study partners will be allowed to assist multiple adults, provided all adults are in the same intervention group. Study partners will be asked to attend all individual support/education sessions, and to support, encourage, and assist participants in complying with the study protocol, such as reminding them to attend the group exercise sessions (RL and RH only), individual support session (all groups) providing opportunities for increased MVPA, and assisting with self-monitoring of MVPA.

MVPA recommendations. We will target 150 min/wk. of MVPA (≥ 3 METs) for all groups as recommended for all adults by the American College of Sports Medicine ¹ and the U.S. Department of Health and Human Services ². MVPA recommendations will progress from 60 min/wk. (3 d/wk., 20 min./d) to 150 min./wk. (5 d/wk., 30 min./d) at the beginning of mo. 4, and remain at 150 min./wk. through the end of the study. Accumulated MVPA in bouts ≥ 10 min will be permitted.

RL and RH Intervention.

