Health educator training/ fidelity

Training. We currently have 3 health educators with experience in delivering group exercise and individual education and support using video conferencing to groups of adults with DS. If needed, new health educators will be trained and will shadow an experienced health educator for a minimum of 3 mos. prior to delivering the intervention on their own. We will conduct weekly meetings with all health educators to discuss issues relative to intervention delivery.

Intervention fidelity. A study team member will review recordings from all scheduled group MVPA and individual support sessions. The content delivered will be compared with a checklist of scheduled activities/topics. Feedback will be provided to all health educators; those covering <80% of scheduled activities/topics will receive additional training and will be dismissed if the problem recurs.

Participant Incentives. Reinforcement systems, known as positive behavioral support programs, have been successful in promoting behavioral change in individuals with DS¹². These strategies provide modest incentives to motivate participants to meet their goals, and were successfully used in our previous trials that included adults with DS^{4, 5, 10}. Participants in all groups who complete self-monitoring of MVPA on 5 of 7 d/wk. will be allowed to choose an iTunes song which will be uploaded weekly to the participant's iPad by study staff. Additionally, to compensate for time and travel, participants will receive \$200 for completion of each of the 3 outcome assessment laboratory visits (baseline, 6, 12 mos.), and \$50 for completion of the additional two accelerometer outcome collection periods (3 and 9 mos.). As an additional incentive, participants will be allowed to keep the iPad and Fitbit on completion of the trial (12 mos.).

Blinding. The nature of this trial precludes blinding of the health educators; however, investigators, data analysts and research assistants will be blinded to condition

ASSESSMENTS

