6.2.2 Enrollment, Baseline, and/or Randomization

Enrollment

Enrollment is defined as the date in which a participant has signed a consent form, passes the DSQIDD turned in a physician consent form.

Baseline Assessments.

Baseline Assessments will take place within two weeks of starting the intervention and will include

- Medication review
- MVPA using accelerometer
- Cognitive Function
- Cardiovascular Fitness
- Quality of Life Questionnaire
- Anthropometrics
- Physical Function (Sub-sample).

- Caregiver Outcomes (Sub-sample).
- Optional practice MRI
- MRI (Sub-sample).
- Adverse Events Review

Randomization

Randomization will take place within 2 weeks before the start the intervention.

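### Assignment is not held until baseline is complete, so the 7-day baseline MVPA can be recorded after the arm is known, and the envelopes go to the role that screens candidates

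*Combined protocol and SAP*

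**What the plan says.** - **Assignment (Sections 5 and 8.1.1).** "Cohorts of ~10-20 participants will be recruited and computer randomized", stratified by sex and age and "sequentially randomized by the study statistician with 2:2:1 allocation to the RL, RH, and UC arms". Then: "Intervention assignments will be concealed in envelopes and delivered to the study coordinator". Neither section says whether the envelopes are sealed, opaque or numbered, who opens them, or when.
- **Screening (Section 4.3).** "The study coordinator will contact the interested individuals by phone to answer questions and conduct an initial eligibility screen". Final eligibility rests on the DSQIID score, and physician clearance is sought separately.
- **Enrollment (Section 6.2.2).** "Enrollment is defined as the date in which a participant has signed a consent form, passes the DSQIDD turned in a physician consent form". Completed baseline testing is not part of the definition.
- **Timing (Sections 6.1 and 6.2.2).** Randomization and baseline have the same two-week window and share one schedule column, KUMC Visit 1, Day -14 to Day -1. No order between them is given.
- **Baseline MVPA (Section 5, Primary Outcome).** The accelerometer is handed out at the baseline laboratory visit, worn for 7 consecutive days and posted back.
- **Analysis (Section 8.3).** Change from baseline is summarized by arm, effect sizes are computed, and a mixed model with group, time and their interaction compares change across arms.
- **Who knows the arm.** Section 8.1.1: "The study team and the participants will not be blinded to group assignment". Section 5: "investigators, data analysts and research assistants will be blinded to condition". Neither names the coordinator.

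**The concern.** The change scores assume that baseline MVPA was measured before the assignment could affect it. If participants and study partners know the arm while the baseline accelerometer is being worn, the baseline itself can respond. Someone told to expect three sessions a week may start moving more. Someone assigned to usual care may move less or stop wearing the device. Either response changes the baseline differently by arm and goes straight into the change scores. The trial exists to supply effect sizes for a later trial, so an error here carries forward.

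The custody arrangement adds a second, weaker worry. The envelopes go to a role that also talks to and screens candidates, and no written safeguard says when they may be opened.

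**Working it through.** **1. The plan's own figures.** 80 × 2/5 = 32 for RH and for RL, and 80 × 1/5 = 16 for UC, as stated in Section 8.1. The precision statements also reproduce. Confidence for ±5 min at SD 10 is 2·T(5/(10/√n); n − 1) − 1, which gives 99.2% (n = 32), 97.8% (24), 93.6% (16) and 88.9% (12), against the stated 99, 98, 94 and 89%. No figure in the plan is disputed.

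**2. The order of events.** Let the baseline visit fall on Day −v, with v from 1 to 14.
- If wear starts on the visit day, the last wear day is −v + 6. It falls before Day 0 only if v ≥ 7, which is 8 of the 14 permitted days.
- If wear starts the next day, the last wear day is −v + 7. It falls before Day 0 only if v ≥ 8, which is 7 of the 14 days.

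So for 6 or 7 of the 14 permitted visit days, the baseline week runs into the intervention. For anyone randomized at that visit, essentially the whole week follows assignment, whatever v is. Nothing in Sections 5, 6 or 8 excludes this.

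One further detail points the same way. Section 5 sends daily wear reminders to participants' iPads in the monitoring week, and iPads are handed out at orientation, which is described separately for the exercise arms and UC. Reminders in the baseline week would presuppose a known arm. The plan does not date orientation, so this is supporting evidence only.

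**3. Effect on the estimate.** Suppose knowing the arm shifts mean baseline by d₁ in an exercise arm and d₀ in UC. The contrast in change becomes the true contrast − (d₁ − d₀). The plan gives no values for d. In SD units, assume the plan's SD of 10 min at both times and a within-person correlation ρ, which the plan does not give. The SD of change is 10·√(2(1 − ρ)).

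| Assumed ρ | SD of change (min) | Shift per 1 min of d₁ − d₀ (SD) |
|---|---|---|
| 0.3 | 11.8 | 0.08 |
| 0.5 | 10.0 | 0.10 |
| 0.7 | 7.7 | 0.13 |

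Effect sizes taken from raw 12-month means would not be touched; those for change would be.

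**4. Predictability, for the secondary risk only.** The block size is not stated, so these figures are illustrations. They also require earlier assignments in the block to be known.
- For a 2:2:1 block of 5, the best guess succeeds with probability 0.400, 0.500, 0.533, 0.600 and 1.000 at slots 1 to 5. The mean is 3.033/5 = 61%.
- In that block the last slot is always certain, and the fourth is certain with probability 2 × (2/5 × 1/4) = 0.2. The certain share is (1 + 0.2)/5 = 24%.
- Blocks of 10 give 56% and 14%, and blocks of 15 give 53% and 10%.
- Without blocks, the best guess is right 40% of the time and no slot is certain.

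**The case against.** The strongest reply concerns entry. A reader might infer that who enters, and when, can depend on the coming assignment. The documents do not support that. Sections 5 and 8.1.1 describe recruiting a cohort and then randomizing it, the statistician does the randomizing, and the assignments are described as concealed. On the plain reading, a cohort's candidates have been screened before their assignments exist. The coordinator's call is only an initial screen, and consent, DSQIID and the physician form already define enrollment. The shared column in Section 6.1 does not show that each person is randomized at their own visit; it is compatible with randomizing a whole cohort shortly before it starts. All of this stands. Selection at entry remains possible only if assignments exist, or can be guessed, before a cohort is fully enrolled. The percentages in step 4 do not show that they can.

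A second reply is that analyzing change already deals with baseline differences. That is fair for genuine differences between people. It does not help when knowledge of the arm has altered the baseline measurement.

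A third is that Section 5 says assessors are blinded. That protects testing in the laboratory, but participants know their arm and their own behavior is what the accelerometer records. None of the three replies supplies a rule that baseline must be complete before assignment.

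**Conclusion.** The point holds in a limited form and should be fixed. As written, the plan allows baseline MVPA, and hence every change score, to be recorded after the arm is known, and it leaves custody and opening of the envelopes undefined in the hands of a role that also screens. It does not establish that either problem will occur. Staff may already finish baseline first.

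The bias cannot be sized from the documents and could go in either direction. One minute of differential baseline shift is worth 0.08 to 0.13 SD of change, if the SD is 10 min at both times and ρ lies between 0.3 and 0.7. This part of the conclusion does not depend on block size or on misconduct. Selection at entry is a secondary and conditional risk.

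**What to change.** In Sections 5, 6.2.2 and 8.1.1, replace the envelope procedure with gated release from REDCap, which already stores the randomization:

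- The statistician keeps the list, stratified by sex and age, in permuted blocks whose sizes are withheld from site staff. Staff who screen or enroll cannot see unused assignments.
- An assignment is released only when consent/assent, DSQIID, physician clearance and all baseline tests due for that participant, including the 7-day accelerometer wear, are recorded as complete. If a cohort is randomized together, this applies to the whole cohort.
- Sections 6.1 and 6.2.2 state that baseline precedes randomization within the window.

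The same amendment should reconcile three related points:
- the blinding statements (Section 5 against 8.1.1);
- the stratification factors (sex only in the Précis and Section 4.3; sex and age in Sections 5 and 8.1.1);
- how adults who share a study partner are assigned, since Section 5 requires them to be in one arm.

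**Cost.** A protocol amendment and REDCap set-up. Scheduling before the start becomes tighter: 7 wear days within a 14-day window leave about a week for the remaining steps, so the visit must fall early or the window be reworded. Incomplete blocks may leave arm sizes slightly different from 32/32/16.

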8.2 Interim analyses and Stopping Rules

No interim analysis of outcomes is planned. We believe this trial conveys minimal risk. Indeed, increased physical activity is desirable and may convey health benefits compared to sedentary behavior. The most likely scenario indicating the need to stop the investigation would be a failure to recruit or deliver the intervention as planned. Another issue relating to stopping rules for this trial could include new information that might become available that would warrant stopping the trial, although this is a remote possibility.

8.3 Data Analyses

Our primary aim is to assess daily MVPA (min.) among the RL, RH, and UC arms at baseline, 3, 6, 9, and 12 mos. and obtain effect sizes for change in MVPA over 12-mos. We will calculate the mean and standard deviation and 95% confidence intervals of daily MVPA at each time point for all 3 groups, as well as for the change from baseline to each time point. This descriptive information will be summarized graphically which will aid in determining if, and when, differences in MVPA arise among and across the 3 groups. The corresponding effect sizes at each time point will be calculated as the differences in the mean divided by the common standard deviation. We will also estimate the correlation of MVPA over time within individuals. This information will be critical to identifying whether single point in time or longitudinal assessments will be utilized to identify the sample size needed for future large-scale confirmatory trials. We will subsequently run a repeated measures ANOVA comparing the change in baseline at each time point across the three groups using a linear mixed model approach with an autoregressive correlation structure over time. The model will include a main effect of group and time and a group by time interaction which will provide an estimate of the treatment effect when modeling longitudinally. The data from this trial will provide solid preliminary data to determine the potential for an effect and inform the best design to employ in subsequent trials.

Our first secondary aim will assess the impact of MVPA across the RL, RH, and UC arms on cardiovascular fitness, quality of life, cognitive function, and brain parameters (whole and regional brain volume, functional connectivity, cerebral blood flow) at baseline, 6, and 12 mos. We will estimate the correlation of change in MVPA on changes in cardiovascular fitness, quality of life, cognitive function, whole and regional brain volume, functional connectivity and cerebral blood flow at 6 and 12 mos. This analysis will be completed with the total sample, irrespective of study arm. Thus 80 participants will provide at least 80% power to detect correlation of 0.31 or higher or -0.31 or lower with a type I error rate of 5%. Sixty subjects (25% loss to follow-up) will still allow us to detect a correlation of 0.36 or higher or -0.36 or lower with 80% power and type I error rate of 5%.

Our second secondary aim will determine the feasibility (retention, session attendance, use of recorded sessions (RH/RL only), and safety) of RL, RH, and UC arms. We will estimate the proportion of participants retained, session attendance, use of recorded sessions and safety, i.e. significant adverse events across the 12 mo. trial, the proportion that adhere to treatment within each arm. Within the RL and RH arms, 32 participants allow us to estimate these proportions with a margin of error no greater than 0.09. Within the UC group, 16 participants will allow us to estimate these proportions with a margin of error no greater than 0.125.

For all analysis we will explore the impact of demographic characteristics such as gender, and racial/ethnic subgroups.

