6.2.4 At-Home Data Collection

- Attendance
 - Session attendance for both group MVPA and individual education/support sessions from baseline to 12 mos. will be obtained from records maintained by the health educator, and expressed as the percent of possible sessions. Attendance at group MVPA sessions will be defined as being logged in to the video conference and remaining on the screen for the entire 30-min session. Attendance at individual support/education sessions, for the both exercise and UC conditions, will be defined as answering the Zoom call, and being present on screen for the entire session.
- Fitbit
 - Daily MVPA will be tracked from the Fitbit device. It will be used by the Health Coaches to provide feedback.
- Exercise Video Recordings:
 - Use of recorded exercise sessions (RL and RH only) will be tracked using Dropbox which provides information on how many times each user watched a video
- Adverse Events
 - As described below, we will ask participants for any adverse events at group exercise sessions and individual education sessions.

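### The primary MVPA means, changes and effect sizes are raw by-visit summaries with no missing-data rule, and the separate mixed model of change does not fully protect against selective loss

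*Combined protocol and SAP*

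**What the plan says.** The primary objective (section 1.1) is to describe daily MVPA in the three arms at five visits and to obtain effect sizes for its change over 12 months. Section 8.3 does this in two separate steps.

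- **By-visit summaries.** "We will calculate the mean and standard deviation and 95% confidence intervals of daily MVPA at each time point for all 3 groups", and the same for change from baseline. Then: "The corresponding effect sizes at each time point will be calculated as the differences in the mean divided by the common standard deviation".
- **Longitudinal model.** A repeated-measures analysis of change from baseline follows, "using a linear mixed model approach with an autoregressive correlation structure over time", with group, time and their interaction, "which will provide an estimate of the treatment effect when modeling longitudinally".

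Section 8.1 gives the precision of an arm mean at full size (32, 32 and 16) and again "allowing for a 25% loss to follow-up", that is, with 24, 24 and 12 participants. It concludes that precision remains adequate. No section defines an analysis set, a missing-data assumption, an imputation rule or a sensitivity analysis.

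**The concern.** A raw mean with no rule for missing values is a mean over whoever has a value. It estimates the arm mean only if having a record is unrelated to MVPA, and the people averaged can change from visit to visit. If the less active, or those who are not improving, tend to stop, the later means or changes look too good.

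The arms also carry different burdens: three group sessions a week, one, or none. Loss may therefore differ between them, and a bias that differs between arms does not cancel in an effect size. Section 8.3 intends these results to guide the design and sample size of confirmatory trials, so an error here is carried forward.

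**Working it through.** **1. The plan's own figures.** Inputs from section 8.1: SD 10 min, margin 5 min, n = 32, 24, 16 and 12. Confidence = 2·T(5√n/10) − 1, where T is the t distribution function with n − 1 degrees of freedom.

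| n | Computed | Stated |
|---|---|---|
| 32 | 99.2% | 99% |
| 24 | 97.8% | 98% |
| 16 | 93.6% | 94% |
| 12 | 88.9% | 89% |

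All four reproduce. They depend on SD and n alone, so they address precision and not bias.

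**2. Sampling error after 25% loss.** The 95% half-width of an arm mean goes from 3.61 to 4.22 min (RH, RL) and from 5.33 to 6.35 min (UC). For RH or RL against UC, the standard error after loss is 10·√(1/24 + 1/12) = 3.54. The half-width goes from 6.16 to 7.19 min, or 0.62 to 0.72 SD.

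**3. Bias by arithmetic.** Bias of an observed-case mean = share missing × (mean of those observed − mean of those missing). The documents give no such gap, so a range is assumed. With 25% missing and gaps of 4, 8 and 10 min/day, the bias is 0.25 × 4 = 1.0, 0.25 × 8 = 2.0 and 0.25 × 10 = 2.5 min/day.

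Between arms with the same gap, the effect size shifts by (difference in share missing) × gap / 10. Equal loss gives zero. Assumed loss of 35% against 15% gives 0.20 × 4/10 = 0.08, 0.20 × 8/10 = 0.16 and 0.20 × 10/10 = 0.20 SD.

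**4. Bias by simulation.** Assumptions:
- five visits, SD 10, drop-out before months 6, 9 and 12, with 25% lost by month 12;
- loss more likely with lower last observed MVPA (level-dependent) or smaller last observed gain (change-dependent), odds ratio 2.0 to 3.3 per SD;
- visit correlation 0.5 or 0.7, either equal between visits or autoregressive.

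This gives 16 settings. Both likelihood fits used an unstructured covariance.

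| Month-12 estimate | Loss mechanism | Bias, min/day |
|---|---|---|
| Raw arm mean | level-dependent | about +0.5 to +1.9 |
| Raw mean change | change-dependent | about +0.7 to +2.0 |
| Likelihood fit to changes only | level-dependent | about −0.15 to −1.3 |
| Likelihood fit to all five visits | either | within about 0.1 |

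End points move by a tenth or two with the details of the drop-out model. Under level-dependent loss, the raw mean change was close to unbiased in these settings. The changes-only model was not, because the level that drives the loss is not among its data. Under change-dependent loss, the changes-only fit is sound, because loss then depends on what it models.

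If one arm is selectively lost and the other is not, 0.7 to 1.9 min/day divided by 10 is 0.07 to 0.19 SD. With step 3, the range is roughly 0.07 to 0.20 SD.

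**5. If loss depends on the unseen value itself.** With 25% missing and log-odds of missingness rising by 1 per SD of lower current MVPA, the observed-case mean is about 2.1 min/day too high. Conditioning on the earlier visit leaves 1.2 to 1.6. A five-visit model therefore reduces this bias but does not remove it.

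**6. Consequence for the next trial.** Required n is proportional to 1/d². As an illustration, a true 0.5 reported as 0.6 gives (0.5/0.6)² = 0.69, about 31% too few participants.

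**The case against.** The strongest objection is that section 8.3 already contains a mixed model. Fitted by likelihood, it uses every available follow-up visit, and the by-visit figures are described there as descriptive. A reader might infer that the primary analysis discards the earlier visits of those who are lost. The documents do not support that: it is true of the by-visit summaries only. What remains is that the effect sizes are defined from the raw means, and that the model takes change as its outcome without baseline as outcome or covariate (step 4). It also drops anyone without a baseline record.

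A reader might also infer that the plan adopts an observed-case rule. It states none; this is read from its silence and from the n = 24 and n = 12 figures.

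On size, the objection largely stands. Similar loss cancels, the documents give no sign of differential loss, and the shift is well inside the sampling error of 0.72 SD.

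A third tempting inference is that the year-long Fitbit record could recover the missing weeks. Section 6.2.4 says: "Daily MVPA will be tracked from the Fitbit device. It will be used by the Health Coaches to provide feedback". Section 5 adds self-monitoring outside sessions, session intensity and, through self-monitoring, the weekly incentive. All of these are parts of the intervention, and section 8 gives the Fitbit no role. Recovery is not shown, for these reasons:

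- The Fitbit is worn on the wrist, while the outcome comes from a hip ActiGraph, and no agreement between them is given.
- People who leave the study may stop wearing it.
- Even a proxy correlated 0.7 with the outcome and available for every missing week would raise the effective UC size only from 12 to 13.7. An imputation model with five predictors fitted within 12 UC participants can lower it (to about 10.7 at R² 0.25).

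Keeping an intervention device out of the outcome analysis is defensible.

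**Conclusion.** The point holds in a limited form. The figures that answer the primary aim have no stated protection against selective loss, and the model beside them gives only part of it. The bias in one arm is up to about 2 min/day at month 12, and the effect-size shift is roughly 0.07 to 0.20 SD if loss differs between arms. It is nil if loss is alike.

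These sizes rest on assumed odds ratios, correlations, gaps and loss patterns, since the documents give only the SD and the 25%. The bias is smaller than the random error, so it does not undermine the trial. It is systematic, however, is passed to the next trial's sample size, and is nearly free to reduce. The change should be made.

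**What to change.** Take the reported arm means, changes, between-arm differences and effect-size numerators at each visit from one likelihood-based repeated-measures model. All five visits, including baseline, should be outcomes, and every randomized participant with any record should be included. The check above used an unstructured covariance. If the autoregressive form is kept, the protection depends on that form being about right.

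State the missing-at-random assumption. Add a simple sensitivity analysis, for example lowering the values predicted for missing visits by a stated amount, such as 4 to 10 min/day, in one arm or in all. Keep the raw means, SDs and plots as description, with the number observed at each visit.

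Fitbit data could at most be an optional, exploratory auxiliary variable, after agreement with the ActiGraph has been checked in weeks when both were worn. It is not part of the main fix.

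The cost is a paragraph in section 8.3 and a little more programming. No new data are needed.
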